STUDY PROTOCOL
May 1, 2017

Project Title: Integrating Safer Conception Counseling to Transform HIV Family Planning Services

NCT03167879

Registered on clinicaltrials.gov on 5/23/17

STUDY PROTOCOL

Overview. This 3-arm, cluster RCT will compare two models for implementing a comprehensive FP program that integrates SCC within current FP services in HIV clinics—an up to 6-session, multi-component, structured SCC intervention (SCC1), and a workshop to train FP providers on use of SCC guidelines (SCC2)—versus existing FP services (usual care). Both SCC1 and SCC2 will use routine screening for fertility desires and a workshop for training FP nurses to implement SCC, but SCC1 is differentiated by its use of a structured counseling SCC protocol and manual (as opposed to the clinical acumen of the trained FP nurses), and inclusion of client outreach and ongoing supervision support. Each arm will be implemented at 2 sites (6 sites in total) and each site will enroll 65 clients (total n=390) with serodiscordant partners who have childbearing desires at recruitment. Participants will be surveyed at baseline, months 6 and 12, and post-pregnancy for those who become pregnant prior to month 12. The primary outcome is correct use of SCM or contraception (depending on desired pregnancy status following SCC consult); secondary outcomes are pregnancy status, PMTCT use (if pregnant), partner seroconversion, and condom use. A cost-effectiveness analysis will also compare the 3 arms to inform policy and practice recommendations for settings of various resource levels.

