- * Discuss other risk reduction options: circumcision (if negative male; available at TASO); sperm washing (available for ~\$1000) and PrEP (available for ~\$120 monthly) are available by referral, but are cost prohibitive for nearly all.
- * Review with client/couple their action plan for the coming month prior to 2nd session.

Follow-up sessions (up to 5 sessions; scheduled after female's menstrual period each month til pregnancy; 20 min):

- * Ascertain how well the client/couple identified the timing of woman's ovulation and used selected SCM.
- * Assess whether calendar, SMS texts and tool kit were helpful; identify strategies to overcome barriers.
- * Assess infected partner's ART adherence and refer for adherence counseling if needed.
- * Use tracking form (see manual) to record success and challenges related to use of SCM.
- * If partner did not attend, and SCM was not used successfully, discuss with client strategies for engaging partner.
- * Pregnancy test if woman's period is skipped; if pregnant, HIV test the partner and start HIV+ mothers on PMTCT.
- * Partner HIV test is done at completion of intervention and again 3 months later to confirm.

If after 6 mos. of correct SCM use pregnancy has not been achieved, SCC is discontinued and the couple referred to fertility clinic for infertility tests. Guidelines call for waiting 12 mos., but they do not account for use of SCM to target the fertile period. Infertility tests (\$70) will be paid for by the study for research participants, so that we can collect data on infertility rates, which are unknown in this population; otherwise, clients will need to pay for these tests.

Arm 2: Training workshop for integration of SCC into FP (SCC2)

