Routinely collected clinic data will be used to analyze FP services in the overall clinic population to examine clinic capacity and fidelity to the intervention. The triage book and childbearing screening item (in SCC1/SCC2 sites) will be used to determine: (a) # who do not want children and % receiving contraception services, and (b) # reporting childbearing desires. FP registries will indicate # new clients receiving FP services (not seen by FP in past year), and % of FP recipients using dual contraception. These will be tracked longitudinally to assess intervention effects on clinic level FP services. % of clients receiving FP referrals after triage will be compared across all 3 arms using research cohort data, since childbearing screening is not used at the usual care site.

Research Participants. The assigned FP programs at each study site will be implemented clinic-wide for all clinic clients, but the 66 study clients enrolled at each site will meet the following **eligibility criteria**:

1. Adults of reproductive age (men age 18-60; women age 18-45).
2. Considering childbearing with their spouse/partner. This will be determined via the triage screening item.
3. Reports having disclosed HIV status to partner. TASO counselors provide clients with assisted disclosure services to help them disclose to partners. Therefore, interested clients who have not yet disclosed their HIV status to their partner will be assisted to do so if they wish, after which they can be considered for enrollment.
4. Partner is HIV-negative. All couples can benefit from SCC and FP, but we focus on discordant couples due to the heightened value of SCC for reducing horizontal HIV transmission. We will use a rapid HIV test to confirm partner's status, and offer the option of a home-based test (a service offered by TASO) if necessary. Confirming the partner's status enables us to accurately assess intervention effects on seroconversion.

ART use is not an eligibility criterion, but SCC will be used to advise and support clients to start and adhere to ART before trying to conceive with SCM. TASO provides ART to all clients in serodiscordant relationships.

Note that only the HIV+ client will enroll in the study and participate in the survey research, not their partners.

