To assess correct SCM use, respondents will be asked if they used TUI, MSI, or sperm washing in the past 6 months and how often. Given the cost of sperm washing, TUI (applicable for all couples) and MSI (applicable for couples in which the male is HIV negative) are the two feasible methods for most clients. Clients will be asked in an open-ended format to describe exactly how they implemented the method. For each method, the interviewer will be looking for 3-5 pre-established pieces of information (e.g., identifying the timing of woman's fertile period; # of days in the fertile period; using condoms outside of the fertile period; collection of semen and insertion using syringe) from the participant's response, which will be used to rate the response as indicating "fully accurate" use of the method, "partially accurate" or no use. Only fully accurate use will be considered correct SCM use for the primary analysis, but the 3-level variable will be examined in secondary analysis. Social desirability may influence responses, but clients are not likely to be able to describe the method in such detail unless they are actually following the procedures. This assessment will occur prior to administering the SCM knowledge part of the survey (which uses a less detailed description of the method) to avoid biasing the measure of SCM use. We will ask about partner use of PrEP and male circumcision, but these methods will not be considered when rating proper SCM use since they are not specific to the context of conception.

Secondary outcomes: (1) achievement of desired pregnancy status and pregnancy outcome [live birth or miscarriage (we will not be able to adequately assess induced abortions due to strong stigma and illegality of such abortions, making it very difficult to get accurate data)] assessed via self-report and chart abstraction; (2) partner seroconversion, with HIV testing at month 12 in addition to testing as part of SCC); (3) PMTCT adherence (enrollment by 14 weeks gestation, ART use during pregnancy and post-delivery, infant ART

prophylaxis, and early infant diagnosis of HIV) for those who become pregnant, assessed via chart abstraction; (4) self-reported consistent condom use in past 6 months (generally for those not seeking childbearing, and all times outside of 3-day fertile period of each month for those seeking childbearing and using TUI/MSI).

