Power analysis: 11% of PLHA in Uganda who want to prevent pregnancy use dual contraception³⁰ and our research shows 15% of PLHA trying to conceive use TUI or MSI.³⁷ Therefore, we expect the usual care arm will have a 15% rate of correct use of contraception/SCM (depending on pregnancy intentions), which is the primary outcome. Using an intra-class correlation (ICC) of 0.01 to control for clustering, based on other studies of reproductive health outcomes,⁷⁴ and 10% attrition at Month 12 (given the 6% in our current study), we will have > 80% power (2-tailed test) to detect a 4.5 percentage point difference (small effect size; $d=.15$) for our comparison of the usual care arm to the combined SCC1 & SCC2 arms on the use of contraception or SCM at month 12, and a 7-8 percentage point difference between the SCC1 and SCC2 intervention arms. In analysis of effects on contraception and SCM use separately, and with half the sample expected to decide to pursue pregnancy and half contraception based on our pilot data, our sample size will provide > 80% power to detect a 6.5 percentage point difference with regards to each of the outcomes when comparing usual care to SCC1 and SCC2 combined, and 8-9 percentage point difference between the SCC1 and SCC2 interventions.

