Data analysis: Our primary analysis will be to compare the combined intervention arms (SCC1 & SCC2) against the usual care control to assess the effects of integrating SCC into FP services, and then compare the outcomes between the two intervention arms to determine whether the more intensive SCC1 shows a larger effect than the less intensive SCC2. The primary outcome-- correct use of contraception/SCM (depending on pregnancy intention)-- will be represented as a binary variable as defined in D.2.3.5, but we will also explore a categorical or continuous outcome derived from frequency of correct use throughout the study. Secondary outcomes to be investigated are pregnancy status, PMTCT use, consistent condom use, and seroconversion of partner. We will use an intent-to-treat approach in the primary analyses; secondary analyses will use only study completers. Participants remain in the study and analysis regardless if their relationship status changes during the study. Attrition weights will be used to account for dropouts, and analyses will incorporate design effects from this weighting in the calculation of standard errors and tests of significance. We will account for clustering, and with only 9 clusters/clinics we will conduct individual level analysis. Regression methods can directly model correlations among units in a cluster (random effects or multilevel models) or more simply adjust standard errors for clustering (GEE, robust standard errors), but these approaches are not reliable with so few

clusters,⁷⁵ so we'll use standard regression methods, but rather than attempt to estimate ICC directly, we will explore the sensitivity of significance levels using a range of plausible ICCs values for the outcomes.

Aim 1: Assess intervention effect on contraception/SCM use: *Hypothesis: Both SCC1 and SCC2 will be superior to usual care, and SCC1 will be superior to SCC2 regarding the primary outcomes.* We'll use logistic regression to compare rates of contraception or SCM use (depending on pregnancy intention) in the SCC1 and SCC2 interventions compared to the control condition, and investigate differences between SCC1 and SCC2 in a separate regression. The models will include covariates to adjust for baseline variables (e.g., childbearing stigma, age, sex) that may differ at baseline and to increase precision of the estimates.

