Aim 2: Assess intervention effect on secondary outcomes (pregnancy status; PMTCT use, consistent condom use, partner seroconversion): We will use the same analytic strategy as described for Aim 1.

Aim 3: Examine eIMB moderators and mediators of intervention effects on SCM and contraception use. We will identify bivariate correlates of the primary outcome from among baseline variables using correlation coefficients, t-tests and chi square tests, followed by a stepwise regression approach to identify a parsimonious list of predictors. We will then use longitudinal analyses to investigate changes in the primary outcome relative to changes in dependent variables such as SCM knowledge, motivation and self-efficacy. Like the baseline cross-sectional analysis described above, we will start with bivariate analyses that will inform a subsequent stepwise regression approach. We will use clinic fixed effects, because with only 9 clinics, clustering standard errors to correct for correlation between patients in the same clinic would significantly reduce power. Robust estimation techniques can adjust for correlation in multiple observations of a given patient over time. We will use a similar analytic approach to examine determinants of the secondary outcomes. Lastly, we will investigate the paths through which the intervention works, and subgroups that benefit more from the intervention. E.g., male clients and their partners may use contraception/SCM more because of their greater control over decision making and ability to secure partner participation in SCC. We can test this hypothesis by adding an interaction term between gender and the intervention. Using methods described by MacKinnon⁷⁶ and others,^{77,78} we will assess whether the intervention has a direct impact on contraception/SCM use or mostly though a mediating variable such as communication with provider about childbearing needs (which may result in clients being more apt to receive the information and encouragement needed to use SCM/contraception).^{46,79}

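### Aim 2 analyses partner seroconversion by covariate-adjusted logistic regression with no sparse-data method; at a rate of about 1% or below, the arm effect will often have no finite estimate

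*Combined protocol and SAP*

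**What the plan says.** Aim 2 covers pregnancy status, PMTCT use, consistent condom use and partner seroconversion, with one sentence of method: "We will use the same analytic strategy as described for Aim 1".

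The strategy it points to is set out under Data analysis and Aim 1:
- Logistic regression of the binary outcome on arm, by standard regression methods.
- Baseline adjustment: "The models will include covariates to adjust for baseline variables", with childbearing stigma, age and sex as examples.
- A separate regression for SCC1 against SCC2.
- Attrition weights, and a check of how significance levels move over a range of plausible ICCs.

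The Measures section lists partner seroconversion as a secondary outcome, tested at month 12 and during SCC. The Power analysis paragraph covers only contraception and SCM use. No seroconversion rate, expected number of events or power appears anywhere, and no exact, penalised or purely descriptive method is named.

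**The concern.** Ordinary maximum-likelihood logistic regression needs events in both groups being compared. If one group has none, the estimated odds ratio for arm is zero or infinite, and its Wald interval and p-value carry no information. If there are no events at all, the arm effect is undefined. Covariates add further ways for the fit to separate. Attrition weights rescale observed couples and cannot fill an empty group. The ICC sensitivity check changes standard errors, not the estimate.

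Protecting the negative partner is why the trial restricts enrolment to discordant couples, so this result will be read closely. If the planned model fails, the replacement would be chosen after the data are seen. If it fits on a handful of events, a non-significant result could be read as evidence that SCC does not affect transmission.

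**Working it through.** The plan states no figure for seroconversion, so there is none to reproduce.

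**Inputs from the documents**
- Sample (Overview): "each site will enroll 65 clients (total n=390) with serodiscordant partners".
- Allocation (Overview): "Each arm will be implemented at 2 sites (6 sites in total". That is 2 × 65 = 130 per arm.
- Retention (Power analysis): "10% attrition at Month 12 (given the 6% in our current study". 390 × 0.9 = 351, so 117 per arm: 117 in usual care and 234 in the pooled SCC arms.

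Other sections mention 66 clients per site and 9 clinics. The Overview figures are used here.

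**Assumed**
- 12-month seroconversion rate p in usual care: 0.5, 1, 2 or 3%.
- SCC either has the same rate or halves it.
- Couples are independent, and every retained couple has a partner test.

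**Formulas**, with q the rate under SCC (q = p or p/2)
- Expected events = 117p + 234q.
- Pooled SCC against usual care: P(at least one empty group) = 1 − [1 − (1−p)^117] × [1 − (1−q)^234].
- SCC1 against SCC2: P(at least one empty group) = 1 − [1 − (1−q)^117]².

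Example at p = q = 1%: 0.99^117 = 0.309 and 0.99^234 = 0.095. Pooled: 1 − 0.691 × 0.905 = 0.37. SCC1 against SCC2: 1 − 0.691² = 0.52. Expected events: 1.17 + 2.34 = 3.5.

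| Usual-care rate | SCC effect | Expected events | Empty group, pooled vs usual care | Empty group, SCC1 vs SCC2 |
|---|---|---|---|---|
| 0.5% | none | 1.8 | 69% | 80% |
| 1% | none | 3.5 | 37% | 52% |
| 2% | none | 7.0 | 10% | 18% |
| 3% | none | 10.5 | 3% | 6% |
| 0.5% | halved | 1.2 | 80% | 94% |
| 1% | halved | 2.3 | 52% | 80% |
| 2% | halved | 4.7 | 18% | 52% |
| 3% | halved | 7.0 | 6% | 31% |

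**Adjusted model.** A simulation with arm plus three covariates (300 runs per scenario, so a Monte Carlo standard error of at most √(0.25/300) = 2.9 points) counted fits with no finite maximum-likelihood solution. At 0.5, 1, 2 and 3%:
- Equal rates: 82, 42, 17 and 3% (pooled against usual care); 88, 67, 23 and 10% (SCC1 against SCC2).
- Risk halved: 88, 63, 28 and 8%; and 94, 88, 61 and 41%.

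**Precision when the model does fit.** Two-sided Fisher exact power at the 5% level, 117 against 234 and before clustering, is 27% for 3% against 1% and 15% for 3% against 1.5%.

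**What an empty arm can show.** With 0 of 117 events, the exact upper 95% limit is 1 − 0.025^(1/117) = 3.1%. This assumes independence. With the power section's ICC of 0.01 and 117/2 = 58.5 couples per site, the design effect is 1 + 57.5 × 0.01 = 1.575. The effective sample is 117/1.575 = 74.3, and the limit becomes 1 − 0.025^(1/74.3) = 4.8%.

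**The case against.** The strongest reply is that the documents give no seroconversion rate, so failure of the model cannot be asserted. The documents also point both ways. Research Participants says ART is provided to all clients in discordant relationships, which suggests a low rate. But ART use is not an eligibility criterion, Study Setting puts about 70–80% of site clients on ART, participants are considering conception, and usual care has no SCC. At 3% with equal rates, the main contrast has an empty group in only 3% of trials. This objection stands, and the point is therefore conditional on the rate.

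Two technical replies also stand in part. A likelihood-ratio test remains computable when a group is empty, but the plan names no test, and that test would still leave no finite odds ratio. Covariates are not the main cause: at 1% with equal rates, 37% of trials have an empty group and 42% of adjusted fits fail. A further reply, that exact intervals ignore clustering, is correct and is taken into the fix.

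A reader might infer more than the documents support:
- *That PMTCT has the same fault.* It is measured only "for those who become pregnant, assessed via chart abstraction", and the follow-up session text refers to HIV-positive mothers: "if pregnant, HIV test the partner and start HIV+ mothers on PMTCT". That is a small subgroup, but PMTCT use need not be rare. With 15 women per arm, the chance that a compared group has one uniform outcome is about 0.5% (SCC1 against SCC2, 0.9%) at an assumed 70% adherence. It becomes frequent only at about 90% or more (24% and 37%).
- *That the plan promises precision.* Research Participants says that confirming the partner's status "enables us to accurately assess intervention effects on seroconversion". This explains why partners are tested at entry. It is a statement about ascertainment, not power, and needs no edit.
- *That this is the trial's main safety result.* The plan lists seroconversion as a secondary outcome and gives it no such label.

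**Conclusion.** The point holds in conditional form, for seroconversion only. At an assumed 12-month rate of about 1% or below, the planned regression will often have no finite arm estimate: an empty group occurs in 37–69% of trials for pooled SCC against usual care and in 52–80% for SCC1 against SCC2, with equal rates. If SCC halves the risk, the second contrast fails about half the time (52%) even when the usual-care rate is 2%. At 2–3% the main contrast usually fits, but on roughly 5 to 11 events, which is too few to tell a useful effect from none.

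These figures rest on assumed rates, 351 tested couples and independence. Partners are not enrolled, so fewer may be tested. That, or positive within-site correlation, would make empty groups more likely. No method of analysis cures the lack of power. The gain is a pre-specified result that can be computed whatever the count and that is not over-read.

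**What to change.** In Aim 2, take seroconversion out of the sentence that refers back to Aim 1, leave the other outcomes there, and specify:

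1. Events and number of partners tested, by arm and by site.
2. Exact (Clopper–Pearson) 95% intervals for each arm's risk, and an exact interval for the risk difference, for both contrasts.
3. A Firth-penalised logistic regression with arm only, as support.
4. Attrition weights kept where the method allows, and a statement of which results are unweighted.
5. Intervals and p-values widened over the same range of plausible ICCs that the Data analysis section already plans, because exact intervals assume independence and are too narrow under clustering.
6. A statement that the result is descriptive, and that a null finding is not evidence of no effect on transmission.

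It would also help to state the assumed rate and expected event count. The cost is SAP wording only, with no change to design, sample or data collection. The downside is that seroconversion has no covariate-adjusted estimate and the exact intervals do not carry the attrition weights.

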Measures. Assessments will include measures of the primary and secondary outcomes and variables that map to our eIMB conceptual framework for understanding use of SCM and contraception, as listed below. Survey measures have been translated into Luganda in our prior research. The survey will be interviewer-administered using computer-assisted software, and administration time is 45-60 minutes.

Primary outcome: Correct use of contraception or SCM over the past 6 months, depending on pregnancy intentions; a single binary indicator will be created for use as the primary outcome, while continuous and categorical measures of frequency and duration of use will be used in secondary analyses. Correct use of contraception is defined as always using both condoms and another modern contraceptive (e.g., oral pills, DEPO injection, IUD implant) (i.e., dual contraception) over the past 6 months (since last survey), and will be ascertained via self-report and chart review (provision of non-condom contraceptive). Male participants will be asked to consent (it won't be required) to the coordinator calling their partner on the phone to assess use of non-condom contraceptives; these data will be kept confidential from the male. This definition is consistent with FP policy and practice in Uganda,⁶⁶ as condoms are important for HIV prevention, but used too inconsistently to prevent pregnancy, hence the need for an added contraceptive. If a participant becomes single or abstinent during the course of the study, avoiding pregnancy and use of contraception will be considered the desired behavior. The primary outcome will define whether SCM or contraception use was consistent (and changed to correspond with changes in pregnancy intentions) with pregnancy intentions over the entire study period.

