Mediators/moderators of primary & secondary outcomes: All draw from our eIMB framework; knowledge, attitudes and beliefs measures were developed by our team and psychometric properties are established.⁶⁷

Mediator/Moderator Variables	Instrument
Demographics: age, sex, education, work. Reproductive history: number of children, pregnancies, miscarriages/abortions HIV/medical characteristics: CD4; viral load; ART use & adherence; clinic attendance; STIs	- self-report developed in-house - self-report developed in-house - chart abstraction (viral load is consistently and routinely done for all patients annually at all sites); self-report; pharmacy refill data (which are highly predictive of viral load in resource constrained settings where all patients get their meds from clinic pharmacy) ⁶⁸
Partner/relationship-related variables: - Partner involvement in PMTCT/SCC/ANC visits - Childbearing desires/intentions - Power in relationship decision making	- self-report developed in-house - self-report developed in-house - Relationship Control Scale; ⁶⁹ alpha=.84
FP services used: Receipt of FP/SCC consults	- self-report developed in-house; chart abstraction
Information: Knowledge of SCM, effective contraception, and risks re. childbearing Motivation: to use SCM and contraception; - Partner willingness to use SCM/contraception Behavioral skills: - Self-Efficacy to use SCM and contraception - Communicate w/ provider re. childbearing needs Ecological (socio-cultural): - Internalized childbearing stigma - Perceived provider stigma of childbearing - Perceived community stigma of childbearing - Perceived cultural pressure for childbearing	- 20 true/false/don't know items developed in-house - 6 items; 10-pt scale; adapted Brief Motivation Scale; ⁷⁰ alpha=.88 ⁶⁷ - 5 items; 5-pt scale; developed in-house; alpha=.85 ⁶⁷ - 5 items; 5-pt scale; adapted from Johnson et al. ⁷¹ alpha=.60 ⁶⁷ - 10 items; adapted from PCAS; ⁷² alpha= .71 - 2 items; 5-pt Likert scale; developed in-house; alpha =.72 - 1 item; 5-pt Likert scale; developed in-house - 3 items; 5-pt Likert scale; developed in-house; alpha =.94 ⁶⁷ - to be adapted from Pezeshki et al. ⁷³

Data Analysis Plan

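### Aim 3 selects predictors by bivariate screening and stepwise regression from up to about 26 candidates with about 58 expected events, so chance predictors and inflated odds ratios are likely; one prespecified, fully reported model would be better.

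*Combined protocol and SAP*

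**What the plan says.** Aim 3 opens with a screening step, which looks for "bivariate correlates of the primary outcome from among baseline variables using correlation coefficients, t-tests and chi square tests". The variables that pass go on to a multivariable step, described as "followed by a stepwise regression approach to identify a parsimonious list of predictors". For the longitudinal analysis of change in the primary outcome, "we will start with bivariate analyses that will inform a subsequent stepwise regression approach". Then: "We will use a similar analytic approach to examine determinants of the secondary outcomes".

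The candidates are in the table introduced as "Mediators/moderators of primary & secondary outcomes: All draw from our eIMB framework". One entry, under partner and relationship variables, is "Childbearing desires/intentions"; the table does not say whose.

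The primary outcome, under Measures, is "Correct use of contraception or SCM over the past 6 months, depending on pregnancy intentions". The Overview puts the relevant intention after counselling: "depending on desired pregnancy status following SCC consult".

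Aim 3 states no entry or removal threshold, multiplicity control, shrinkage or internal validation, and does not label the selection exploratory.

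**The concern.** When the same data choose the predictors and then estimate their effects, the p-values and intervals from the final model take no account of the choosing. Noise variables survive, true but modest predictors are often dropped, and those that survive look stronger than they are. Few events per candidate make this worse, and each rerun at another stage or for another outcome adds opportunities for chance findings.

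At stake is the reading of Aim 3: which eIMB constructs are reported as related to use of safer conception methods (SCM) or contraception, and how strongly.

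A second, smaller matter is that pregnancy intention decides which behaviour is scored in the primary outcome. If the client's own intention is also a predictor, its coefficient partly compares how hard two scoring rules are to meet.

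**Working it through.** The plan gives no figure for Aim 3, so there is none to reproduce.

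**Candidates.** Counting the mediator/moderator table: demographics 4, reproductive history 3, HIV/medical 6 (ART use and adherence counted separately), partner/relationship 3, FP services 1, information 1, motivation 2, behavioural skills 2, ecological 4. The total is 26. It is 25 if ART use and adherence are one item, and more if scales are split into SCM and contraception parts.

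**Events.** The Overview gives 390 clients. The power analysis gives a 15% rate for usual care, 11% for dual contraception among those preventing pregnancy, and 10% attrition at month 12.
- Baseline at 15%: 390 × 0.15 = 58.5 events; 58.5 / 26 = 2.25 per candidate.
- Baseline at 11%: 390 × 0.11 = 42.9; 42.9 / 26 = 1.65.
- After attrition at 15%: 351 × 0.15 = 52.65; 52.65 / 26 ≈ 2.0. An effective intervention would raise this.

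**Chance selection, closed form.** For k independent null candidates each tested at 0.05, the chance of at least one false positive is 1 − 0.95^k.
- k = 26: 1 − 0.95^26 = 73.6%; expected number 26 × 0.05 = 1.3.
- k = 18: 60.3%; expected number 0.9.

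**Chance selection, simulation.** N = 390, 15% outcome, 26 continuous null candidates, t-test screen, then backward-elimination logistic regression. All thresholds are assumptions.

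| Screen / stay | Candidate correlation 0 | Candidate correlation 0.3 |
|---|---|---|
| 0.05 / 0.05 | 73% | 61% |
| 0.10 / 0.05 | 73% | 65% |
| 0.20 / 0.05 | 73% | 77% |
| 0.20 / 0.10 | 95% | 90% |

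Entries are the share of datasets retaining at least one chance predictor. At stay 0.05 the mean number retained is 0.7 to 1.4. Retained null predictors show a typical odds ratio of about 1.4 to 1.5 per SD.

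**Inflation, one true predictor among 26** (correlation 0 and 0.3 respectively).
- True OR 1.2: kept in 24% and 18% of datasets; mean when kept 1.45 and 1.49.
- True OR 1.3: kept in 46% and 35%; mean when kept 1.48 and 1.52.
- True OR 1.5: kept in 80% and 66%; mean when kept 1.58 and 1.59.

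**The alternative.** A prespecified eight-variable model with every estimate reported recovers a true OR of 1.30 as 1.31 on average, with about 95% interval coverage. It shows any false positive at 0.05 in about 31-33% of datasets.

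**Intention.** The power analysis gives 11% for those preventing pregnancy and 15% for those trying to conceive: 15 − 11 = 4 points. With the expected half-and-half split (195 per group), power to detect that gap is about 22%.

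**The case against.** The strongest reply is that these harms are not peculiar to stepwise selection. With n = 351 and all 26 null candidates in one full model, without selection, at least one reaches p<0.05 in 77% of runs. A single true predictor of OR 1.30 tested alone is significant in 42% of runs and averages 1.51 when it is. That stands: the false-positive rate is mostly multiplicity and the inflation mostly significance filtering. It does not rescue the procedure, because screening and stepwise selection report only what passes the filter. A shorter prespecified model has fewer chances to err and shows every estimate.

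It is also fair that 26 is an upper count. Aim 3 speaks of baseline variables, and Recruitment places the baseline survey before the first SCC consult, so receipt of SCC can hardly vary then. The longitudinal stage concerns change in variables such as knowledge, motivation and self-efficacy, which excludes fixed demographics. Framework-derived measures are unlikely all to be null. These points soften the figures; at 18 candidates the closed form is still 60%.

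A reader might infer that intention defines the outcome and so guarantees an association. The documents do not support that. Intention selects the behaviour to be scored, and a client with either intention can be scored correct or incorrect. An association arises only as far as the two criteria differ in difficulty, which is 4 points on the plan's own rates, though the gap could be larger in the intervention arms. All clients are considering childbearing at enrolment, so baseline intention varies little, and the table's item may refer to the partner.

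A reader might also infer that the pathway conclusions come from the stepwise list. They do not: Aim 3 describes mediation and the gender interaction separately.

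**Conclusion.** The point holds for the selection method. Under assumed thresholds of p<0.10 to screen and p<0.05 to stay, and no true predictors, about 65-73% of datasets of 390 retain a chance predictor. Varying the screen from 0.05 to 0.20 gives 61-77%. A true OR of 1.30 per SD is kept in fewer than half of datasets and averages about 1.5 when kept. These figures are for one outcome at one stage. They assume a 15% rate, continuous candidates and a full pool of 26.

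A chance predictor is therefore likely, not certain, and the documents do not support calling the output mostly chance or blaming stepwise selection for all of the inflation. For intention, the supported point is narrow: it sets the scoring rule, so its coefficient needs separate handling. The randomised comparisons in Aims 1 and 2 are untouched. This is an inexpensive improvement to a supporting aim, not a threat to the trial's main conclusion.

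**What to change.** - Replace screening and stepwise selection with one prespecified model containing knowledge, motivation, self-efficacy, provider communication, partner willingness and stigma, plus age and sex. Keep every term and report every estimate with its interval.
- State which stigma scale or scales enter. If stigma is one term, the model has eight, or 58.5 / 8 ≈ 7.3 baseline events per term before any clinic effects.
- Use the same prespecified list, in change form where that makes sense, for the longitudinal analysis and the secondary outcomes.
- Label any analysis of the longer list exploratory. Penalised regression with bootstrap selection frequencies is one option; report no stepwise p-values.
- State whose intention the table's item measures. Keep the client's own intention out of the predictor list, or report it separately with a note that it sets the scoring rule. Stratifying by intention is possible but halves the data: at n = 175 with eight predictors, a true OR of 1.30 reached significance in 23% of runs and averaged 1.84 when it did.

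The cost is plan wording and modest analysis time, with no new data. The predictor list will be longer, the intervals wider, and about a one-in-three chance of some false positive among the eight terms remains, so the estimates should be read as a set.
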